1. INTRODUCTION

1.1 BACKGROUND AND STUDY RATIONALE

The NO-sGC-cGMP (nitric oxide – soluble guanylate cyclase – cyclic guanosine 3',5'-monophosphate) pathway plays a critical role in the cardiovascular system. In the vascular endothelium, sGC is stimulated by NO to produce cGMP, which acts on downstream targets including cGMP-dependent protein kinases, phosphodiesterases, and ion channels. This leads to relaxation of the vascular smooth muscle and vasodilation. In addition, intracellular cGMP is involved in processes that affect vascular proliferation, fibrosis, and inflammation. Impaired NO-sGC-cGMP signaling, has been implicated in the pathogenesis of cardiovascular diseases such as systemic and pulmonary hypertension, coronary artery disease, congestive heart failure, peripheral vascular disease, atherosclerosis, and kidney disease. Agents that stimulate sGC to increase cGMP production (1,2) may be useful for treating and/or preventing a broad range of diseases that may ensue from dysfunction in the fundamental NO-sGC-cGMP pathway.(3,4)

This exploratory, proof-of-concept study will evaluate the safety, tolerability, PK, and PD of 2 dosing regimens of daily 40 mg IW-1973 administered orally for 2 weeks to patients with type 2 diabetes mellitus and hypertension. This study is designed to explore the tolerability profile of the MAD MTD, 40 mg IW-1973, in a patient population, and to explore whether tolerability can be improved with an initial week of BID dosing.

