3.5.3 Selection of Dosage in the Study

This Phase 2a exploratory study will evaluate 40 mg IW-1973 administered daily for 2 weeks according to 2 different regimens: QD for both weeks or BID for the 1st week and QD the 2nd week. In the Phase 1b MAD study ([ICP-1973-102](#)), 40 mg IW-1973 was considered the maximum tolerated repeat dose, therefore, 40 mg was chosen for evaluation in this patient population.

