3.7.3.9 Recording Adverse Events

Adverse events will be collected and recorded from the time the patient signs the ICF at the Screening Visit through the End of Trial Visit. All AEs, regardless of the assumption of a causal relationship with study procedures or study medication, must be recorded in the patient's source documentation and subsequently on the appropriate AE page of the patient's eCRF. This record includes AEs the patient reports spontaneously, those observed by the Investigator, and those elicited by the Investigator in response to open-ended questions during the study, such as "Have you had any health problems since your last visit?"

For every AE, the Investigator must

- Provide an assessment of the severity, causal relationship to the study medication, and seriousness of the event
- Document all actions taken with regard to the study medication (ie, no action taken, treatment temporarily interrupted, or treatment discontinued)
- Detail any other treatment measures taken for the AE, including concomitant medications and/or procedures

Pretreatment AEs will be collected from the time the patient signs the ICF until the patient receives study drug. Pretreatment AEs will be captured in the patient's source documentation but will only be entered for patients who receive study drug on the AE page of the patient's eCRF.

Laboratory abnormalities and changes in vital signs, physical examination findings, and 12-lead ECG parameters should be considered AEs and reported on the AE page of the patient's eCRF if the Investigator considers them clinically significant and/or they necessitate intervention.

Any medical condition that is present when a patient is screened and does not worsen in severity and/or frequency should be reported as Medical History and not as an AE. However, if the condition does deteriorate in severity and/or frequency at any time during the study, it should be reported as an AE.

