3.9.3.4 Safety Analyses

3.9.3.4.1 Adverse Events

Adverse events will be coded using the latest version of Medical Dictionary for Regulatory Activities (MedDRA) available at the start of the study. Treatment-emergent adverse events (TEAEs) are those AEs that started or worsened in severity after the administration of study drug. All TEAEs as well as those that occurred during the first 7 days of treatment will be summarized by system organ class (SOC) and preferred term (PT) for each treatment group. In addition, listings of severe TEAEs, drug-related TEAEs, SAEs, AEs leading to study discontinuation, and AEs leading to death (if any) will be provided.

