7.9.1 Adverse Events

All adverse events (AEs) will be coded using the Medical Dictionary for Regulatory Activities (MedDRA) Version 19.1 and will be classified by MedDRA system organ class (SOC), and preferred term (PT).

Treatment-emergent adverse events (TEAEs) are those AEs that started or worsened in severity after the administration of study drug. If it is not possible to determine when the event started due to incomplete start dates/times, it will be assumed to be treatment-emergent.

The number and percentage of patients who experience at least one TEAE as well as those who experience each specific SOC and PT will be presented by treatment group as well as for IW-1973 overall using the Safety Population. TEAEs will also be summarized by week, where TEAEs that started during Week 1 (study days 1-7) or Week 2 (study days 8-14) will be presented by treatment group for the respective week. Summaries of study drug-related TEAEs will also be presented by treatment group. For presentation of AE incidence, AEs will be sorted alphabetically by SOC, and within each SOC, by decreasing incidence of PT in the overall group.

In addition, AEs in screen failure patients, TEAEs, severe TEAEs, study drug-related AEs (those that are determined by the Investigator to be related to study drug), serious AEs, AEs that resulted in study discontinuation, and AEs that resulted in death (if any) will be presented in separate listings.

Adverse Events of Clinical Interest

Since an increased risk for bleeding may represent a class effect with sGC stimulators, bleeding events and TEAEs related to bleeding will be summarized by treatment group and presented in a data listing. Similarly, TEAEs associated with hypotension or lowering of BP will be summarized by treatment group and presented in a data listing. See [Appendix 1](#) for details on the determination of the events for each category of interest.

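### The by-week TEAE summary sorts events by start date only, so worsening that the TEAE definition includes can be missing from that table

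*SAP*

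**What the plan says.** SAP 7.9.1 says that TEAEs "are those AEs that started or worsened in severity after the administration of study drug". It plans an overall summary by treatment group: "The number and percentage of patients who experience at least one TEAE as well as those who experience each specific SOC and PT". It then adds a summary by week, made up of "TEAEs that started during Week 1 (study days 1-7) or Week 2 (study days 8-14".

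Protocol 3.9.3.4.1 plans a narrower split, by SOC and PT: "All TEAEs as well as those that occurred during the first 7 days of treatment will be summarized by system organ class (SOC) and preferred" […]. It has no separate Week 2 summary, and it speaks of events that occurred rather than started. SAP Section 8, which lists departures from the protocol's analyses, does not mention the by-week rule.

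The weekly split follows the design. Protocol 3.5.3 describes the regimens as "QD for both weeks or BID for the 1st week and QD the 2nd week", and Protocol 1.1 says the study is meant "to explore whether tolerability can be improved with an initial week of BID dosing".

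**The concern.** The definition has two limbs, onset and worsening. The by-week rule uses only the first, so an event that is a TEAE because it worsened has no week assigned on that ground.

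This matters because the by-week table is the only planned AE summary divided at Day 8, when the BID/QD arm changes regimen. A reader asking how events behaved before and after that change will look there. If a mild event from Week 1 becomes moderate in Week 2, the Week 2 column shows nothing for it. The overall table does not show the change either, because that patient is already counted.

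**Working it through.** The plan states no figure to reproduce; the sample size was set outside statistical considerations (SAP 4). The check is a reading of the rule, followed by simple arithmetic on its weight.

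**Step 1. Follow each type of event through the rules in SAP 7.9.1, with one record per AE.**

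| Event | TEAE? | Overall table | Week 1 | Week 2 |
|---|---|---|---|---|
| Starts in Week 1, no worsening | Yes | Counted | Counted | Not counted |
| Starts in Week 1, worsens in Week 2 | Yes | Counted once | Counted | **Not counted** |
| Starts before Day 1, worsens in Week 1 | Yes | Counted | **Not counted** | Not counted |
| Starts before Day 1, worsens in Week 2 | Yes | Counted | Not counted | **Not counted** |
| Starts on Day 1 before the dose, worsens in Week 1 | Yes | Counted | Counted (start day is Day 1) | Not counted |

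The bold cells are the loss. Pre-Day-1 records will exist: Protocol 3.7.3.9 collects AEs from consent and enters pretreatment AEs on the eCRF for patients who are dosed.

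**Step 2. Is a worsening re-entered with its own date?** Three places come close.

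- Protocol 3.7.3.7 counts clinically significant worsening of a preexisting condition as an AE.
- Protocol 3.7.3.9 says of a condition present at screening that "if the condition does deteriorate in severity and/or frequency at any time during the study, it should be reported as an AE". Such a condition was medical history, so the AE record is new, although no start date is prescribed.
- Protocol 3.7.3.7.2 asks for a severity rating for each AE.

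None says that an AE arising after screening, or on treatment, is closed and re-entered when it becomes more severe. SAP 9.2 counts each patient once per SOC, per PT and overall. For summaries by severity it keeps the highest grade, with no reference to time.

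**Step 3. Weight of one patient.** Inputs: 26 patients, allocated 5:5:3 (Protocol 3.9.1), assumed all dosed and all in the denominator.

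- Active arms: 26 × 5/13 = 10 each. Placebo: 26 × 3/13 = 6.
- One patient: 1/10 = 10 points in an active arm, 1/6 = 16.7 points on placebo, and 1/20 = 5 points in a pooled IW-1973 column.
- This applies only if the patient has no other qualifying event in that cell.

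**Step 4. Illustration with assumed counts** (not from the documents), for any TEAE in one arm of 10. Four patients have an event starting in Week 1, and two of these worsen in Week 2. One other patient has an event starting in Week 2. One other has a pre-Day-1 event that worsens in Week 1.

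- Start only: Week 1 = 4/10 = 40%; Week 2 = 1/10 = 10%.
- Start or worsen: Week 1 = (4 + 1)/10 = 50%; Week 2 = (1 + 2)/10 = 30%.
- Overall table, either rule: (4 + 1 + 1)/10 = 60%.

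**Step 5. Chance that an arm of 10 has at least one affected patient,** 1 − (1 − p)^10, for assumed p: 40% at p = 5%, 65% at p = 10%, 89% at p = 20%. The documents give no value for p.

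**The case against.** The best reply is that the definition decides which events are TEAEs and the weekly rule merely sorts them by onset, which is a coherent way to build an incidence table. The study is exploratory, SAP 6.6 calls the safety analyses qualitative, and no decision rule uses this table. The eCRF completion instructions and the table specifications are separate documents and may already settle how worsening is dated. If each worsening is a new record, the start-only rule captures it.

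Much of this stands. It limits the importance of the point and makes the effect conditional. It does not remove the gap: on the text available, the treatment of worsening by week depends on an unstated recording practice, at up to 3 centers.

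A reader might infer more than the documents support:

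- *That these events leave the tolerability comparison.* They do not. They remain in the overall TEAE table and the listings and, where they apply, in the drug-related, bleeding and hypotension summaries, none of which is limited by start week. An event that began in Week 1 also stays in the Week 1 column.
- *That the rule favours BID/QD.* It is identical in every arm. Missing Week 2 worsening could flatter BID/QD after its regimen change. Equally, missing Week 1 worsening of pre-Day-1 events could flatter QD/QD, which takes 40 mg once daily from Day 1. No net direction is shown.
- *That Week 1 against Week 2 is the deciding analysis.* No section says so. The question in Protocol 1.1 is also served by comparing arms in Week 1 and overall.

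**Conclusion.** The point holds in a limited form. As written, the by-week table is incomplete by the SAP's own TEAE definition: it omits pre-Day-1 AEs that worsen on treatment from both weeks, and omits from Week 2 the worsening of AEs that began in Week 1. This rests on one assumption, that a worsening is not entered as a new AE with its own start date. Neither document requires such entry, and neither rules it out.

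The step size is known, at 10 points per affected patient in an active arm and 16.7 on placebo with full arms. The number of affected patients is not, so the percentages in the illustration are not a forecast. No overall TEAE incidence changes. The point is worth correcting because the table concerned is the only AE summary split at the regimen change, and the correction is small.

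**What to change.** Reword the by-week sentence in SAP 7.9.1 so that a TEAE belongs to Week 1 (study days 1-7) or Week 2 (study days 8-14) if it either began or increased in severity in that week. Assign it by the date of onset or of increased severity, and say explicitly that a patient may count in both weeks. State alongside it that an increase in severity after dosing is entered as a new, dated AE record. Without that date the new rule cannot be programmed.

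The cost is about one SAP sentence and one data-entry convention, settled before unblinding. Some AEs will be counted in both weeks, so the weekly columns will not add up to the overall column; a table footnote can say this. Overall patient incidence is not inflated by the extra records, because SAP 9.2 counts each patient once per SOC, PT and overall.

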7.9.2 Clinical Laboratory Parameters

For each quantitative clinical laboratory parameter, descriptive statistics of the observed values (in derived SI units) as well as change from study baseline will be presented overall for each assessment timepoint for the safety population.

Parameter values will also be categorized as low, normal, or high based on reference ranges provided by the lab, and shifts from baseline to each later timepoint will be tabulated. If there is more than one measurement for a lab parameter at a postbaseline timepoint, only the last measurement will be used.

Listings of laboratory parameters will be included.

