If plasma concentrations of IW-1973 are detected, the PK parameters will be determined and tabulated, and summary statistics will be reported by treatment group.

Safety Analyses

Adverse events (AEs) will be summarized by system organ class (SOC), preferred term (PT), and treatment. Listings will be provided for severe AEs, drug-related AEs, SAEs, and AEs leading to study discontinuation. Descriptive statistics will be calculated on the safety parameters (ECG, vital signs, and clinical laboratory tests, eGFR, UACR) by treatment.

ELIGIBILITY CRITERIA

INCLUSION CRITERIA

Patients must meet all of the following criteria to be eligible for enrollment in this study:

1. Patient has signed an ICF before any study-specific procedures are performed.
2. Patient is an ambulatory male or female aged 30 to 75 years at the Screening Visit.
3. Female patient is not pregnant or breastfeeding at the time of the Screening Visit and Check-in. Negative serum pregnancy tests must be documented at the Screening Visit and at Check-in before dosing.
4. Female patients must be postmenopausal (no menses for 12 consecutive months), surgically sterile (ie, bilateral oophorectomy, hysterectomy, or tubal ligation), or, if of childbearing potential, agree to use 1 of the following methods of birth control from the date they sign the ICF until after the End of Trial Visit:
 - a. Combination of 2 highly effective birth control methods (eg, condom with spermicide plus intrauterine device, condom with spermicide plus a diaphragm or cervical cap, hormonal contraceptive [including progesterone implant] combined with a barrier method)
 - b. Maintenance of a monogamous relationship with a male partner who has been surgically sterilized by vasectomy (vasectomy procedure must have been conducted \geq 60 days before the Screening Visit or confirmed via sperm analysis) plus a hormone or barrier method
5. Patient's body mass index (BMI) score is > 20 and $< 40 \text{ kg/m}^2$ at the Screening Visit.

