3.9.3 Statistical Methods

3.9.3.1 General Considerations

Continuous variables will be summarized using the mean, standard deviation, minimum, median, interquartile range, and maximum. Categorical variables will be summarized using the frequency and percentage of patients in each category. Data summaries will be presented by treatment group.

Inferential statistics, if calculated, will only be used for descriptive purposes.

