3.9.3.4.2 Vital signs, ECGs, and Clinical Laboratory Tests

Vital signs, 12-lead ECGs, and clinical laboratory evaluations (including clinical chemistry, hematology, coagulation, urinalysis, and UACR) at each assessment timepoint and the change from study baseline at each postdose timepoint will be summarized by treatment group.

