6. STATISTICAL METHODS

6.1 GENERAL METHODOLOGY

Descriptive statistics (number of patients, mean, standard deviation, median, 25th and 75th percentiles, minimum and maximum) will be calculated for continuous variables. For summaries of continuous PK parameters, the geometric mean and the coefficient of variation (CV) will also be presented. For categorical variables, frequencies and percentages for each category will be presented. Percentages will be based on the total number of patients with non-missing values. If there are missing values, the number missing will be presented, but without a percentage. Data from screen failure subjects will be presented in subject data listings.

Inferential statistics, if calculated, will only be used for descriptive purposes.

All statistical analyses will be performed using SAS[®] Version 9.3 or later (1). Additional analyses using alternative software may be performed as part of the PK analysis.

Summary data for safety, PD and PK parameters will be presented by treatment group and IW-1973 overall, unless otherwise indicated:

- Placebo
- IW-1973 40 mg Total Daily Dose BID/QD
- IW-1973 40 mg Total Daily Dose QD/QD
- IW-1973 40 mg Total Daily Dose Overall

Summary data for PK parameters on Day 1 will be presented only for the 2 active treatment groups.

Definition of Baseline:

The following definitions of baseline will be used to calculate change from baseline parameters, unless specified otherwise:

- Study baseline is defined as the last non-missing assessment before first administration of study drug.

- For PD parameters obtained from ambulatory BP monitoring, time-matched baseline is calculated using the predose assessments on Day -1 that correspond to the respective postdose assessment timepoints.
- Trough baseline for supine BP and pulse assessments is defined as the Day 1 AM predose assessment.

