7.9.6 ECG Parameters

For each ECG parameter, descriptive statistics of the observed values as well as change from study baseline will be presented overall for each assessment timepoint for the safety population. Shift tables from study baseline to the discharge visit (Day 15) for the overall ECG interpretation (normal, abnormal not clinically significant, or abnormal clinically significant) will be summarized for all subjects in the Safety population.

ECG parameters will also be presented in a data listing.

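### SAP 7.9.2 and 7.9.6 present laboratory and ECG descriptive statistics 'overall', where the protocol requires them by treatment group, and SAP Section 8 declares no change

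*SAP*

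**What the plan says.** The protocol is consistent on this point.

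- General rule (Protocol 3.9.3.1): "Data summaries will be presented by treatment group".
- For vital signs, ECGs and laboratory tests, Protocol 3.9.3.4.2 says that "the change from study baseline at each postdose timepoint will be summarized by treatment group".
- Protocol synopsis, Safety Analyses: "Descriptive statistics will be calculated on the safety parameters (ECG, vital signs, and clinical laboratory tests, eGFR, UACR) by treatment".

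The SAP begins the same way. Section 6.1 states: "Summary data for safety, PD and PK parameters will be presented by treatment group and IW-1973 overall, unless otherwise indicated". It then lists placebo, the two IW-1973 regimens and one pooled column, "IW-1973 40 mg Total Daily Dose Overall".

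Two safety sections read differently. SAP 7.9.2 says of the laboratory parameters that observed values and "change from study baseline will be presented overall for each assessment timepoint for the safety population". SAP 7.9.6 says: "For each ECG parameter, descriptive statistics of the observed values as well as change from study baseline will be presented overall". It adds that the ECG shift table from study baseline to Day 15 "will be summarized for all subjects in the Safety population". Neither section mentions treatment group.

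SAP Section 8 lists several added analyses and three changes: the population for standing and orthostatic blood pressure and pulse, a unit in the HOMA-IR formula, and the dropping of Day 1 AUC to infinity. None concerns how laboratory or ECG results are grouped.

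**The concern.** The stated objective is to compare the safety and tolerability of two regimens, in a trial with a placebo arm. A laboratory or ECG summary that is not split by arm cannot serve that comparison. A programmer who follows 7.9.2 and 7.9.6 as written would depart from the protocol without any record of the departure.

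ECG is the more exposed of the two, because 7.9.6 is the only section of the SAP that analyses it. Among the laboratory tests, haemoglobin, haematocrit, aPTT, prothrombin time and INR would have no arm-level means or changes anywhere, although SAP 7.9.1 names bleeding as a possible class effect.

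**Working it through.** The plan gives no figure to reproduce here: the sample size was set outside statistical considerations. The check is a comparison of texts, followed by a count of what is affected.

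**1. Does SAP 6.1 resolve the conflict?** Its default covers safety parameters but applies only where nothing else is indicated. 7.9.2 and 7.9.6 do state a form of presentation, so on a plain reading they displace the default. The neighbouring sections name treatment groups: 7.9.1 (adverse events), 7.9.3 (eGFR), 7.9.4 (UACR) and 7.9.5 (vital signs). Section 7.9.1 asks for treatment groups and also for IW-1973 overall, so where the SAP wants both it can say both.

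**2. What would be pooled?** 26 patients at 5:5:3 give 26 × 5/13 = 10, 26 × 5/13 = 10 and 26 × 3/13 = 6. The Safety Population is therefore 20/26 = 76.9% active and 6/26 = 23.1% placebo. A mean change of d on active drug and 0 on placebo would appear as (20 × d + 6 × 0)/26 = 0.77d, with no comparator beside it.

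**3. Which laboratory analytes are affected?** Counted from SAP 5.2:
- Chemistry: 23 listed. Six have arm-level means or changes elsewhere: cholesterol, HDL, LDL and triglycerides (7.7), glucose through fasting plasma glucose (7.7), and creatinine through eGFR (7.9.3). 23 − 6 = 17.
- Haematology: 14 listed, taking the differential as 5 cell types. Platelet count is covered in 7.7. 14 − 1 = 13.
- Coagulation: 3 listed, none covered elsewhere.
- Total affected: 17 + 13 + 3 = 33 of 23 + 14 + 3 = 40, or 82.5%. Counting the differential's percentages and absolute values separately adds 5 to each number: 38 of 45, or 84.4%.

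Quantitative urinalysis results are affected too but are not in the count.

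**4. At which timepoints?** The Schedule of Events has two postdose full laboratory panels (Day 15 and Day 42) and two postdose ECGs (Day 1 at 4 hours, and Day 15).

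**5. What stays by arm?** The laboratory shift tables in 7.9.2 name no grouping, so the 6.1 default applies to them. The following also stay by arm: eGFR and UACR; fasting glucose, insulin, HbA1c and lipids; VerifyNow results, platelet activation markers and platelet count; and adverse events, including the bleeding category. Laboratory and ECG listings are planned as well.

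**6. How precise would arm-level means be?** For active (10) against placebo (6), the standard error of a difference in mean change is s × √(1/10 + 1/6) = 0.52s, where s is the SD of the change. If r is the correlation between baseline and postdose values, s = SD × √(2(1 − r)). The documents give no r, so it is assumed over a range. With t = 2.145 on 14 df, the 95% half-width is:
- r = 0.5: 2.145 × 0.516 × 1.00 = 1.1 SD
- r = 0.8: 2.145 × 0.516 × 0.632 = 0.7 SD
- r = 0.9: 2.145 × 0.516 × 0.447 = 0.5 SD

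**The case against.** The best defence is that no pooling was intended. SAP 6.1 sets the display for all safety parameters, and when it narrows a display, as for Day 1 PK, it says so with the word 'only'. Sections 7.9.2 and 7.9.6 contain no such word. SAP 7.1 groups the Safety Population by drug actually taken. Section 8 goes down to a unit typo, so its silence on a larger change suggests that none was meant. Pooled laboratory means next to by-arm shift tables within one section would also be an odd plan. SAP Section 1 puts the table specifications in a separate document, which may already be by arm.

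All of this makes loose drafting plausible, and intent cannot be settled from the two documents. It does not remove the conflict. If by-arm display is intended, the wording is wrong; if it is not, a departure from the protocol is undeclared.

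The defence is also right that the loss is limited. Bleeding is still examined by arm through adverse events and platelet function. In a study with 26 patients, descriptive aims and full listings, by-arm tables can be produced later.

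A reader might infer three stronger things that the documents do not support:
- That 'overall' means the one overall column defined in 6.1, so that placebo is left out. Both sections specify the Safety Population, which includes placebo patients.
- That the ECG shift table is certainly pooled. Its wording may only name the population.
- That by-arm means would readily reveal a modest drift. With 10 against 6 patients the half-width is about 0.5 to 1.1 SD, so a change of 0.5 SD would usually not stand out.

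**Conclusion.** The point holds as a conflict of wording between the SAP and the protocol that Section 8 does not declare. Taken literally, it removes arm-level means and changes for all ECG parameters and for 33 of 40 chemistry, haematology and coagulation analytes (38 of 45 on the finer count), and it mixes 20 active with 6 placebo patients. These counts show how far the sentences reach; they do not measure harm. They treat creatinine and glucose as covered by eGFR and fasting plasma glucose.

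The case is stronger for ECG, which has no other analysis section, than for laboratory tests, where by-arm shift tables and several by-arm summaries remain. By-arm tables in arms of 10, 10 and 6 would be imprecise, but they are what the protocol specifies and what the safety comparison needs. Confidence that the text needs correcting is high; whether pooling was intended is unknown.

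**What to change.** - In SAP 7.9.2 and 7.9.6, replace 'presented overall' with *presented by treatment group and IW-1973 overall*.
- In 7.9.6, state that the ECG shift table is also by treatment group and IW-1973 overall, in the Safety Population.
- Check that the separate table specifications agree.
- If a pooled display is really intended, declare and justify it in Section 8.

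This should be settled before unblinding. It costs SAP wording and extra columns in tables already planned; data collection does not change.
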